7.2.3. Patient stratification

Analyses will be stratified by:

- IMDC risk category (defined at the initiation of the first treatment for the metastatic RCC; see Table 1 and listing below for definitions)
 - Applied to all primary and secondary objectives
- Treatment line
 - Applied to primary objective 2 and 3

IMDC risk factors (each criterion accounts for +1 for the risk score):

1. Less than a year from time of initial RCC diagnosis to initiation of treatment for the metastatic RCC

2. Performance status* <80% (Karnofsky)
3. Hemoglobin* below normal (women < 117 g/l; men < 134 g/l)
4. Serum calcium* above normal (> 2.51 mmol/l)
5. Neutrophiles* above normal (> 6.3 x 10⁹/l)
6. Thrombocytes* above normal (> 350 x 10⁹/l)

** for performance status and laboratory values data of ± 3 months around the treatment initiation will be utilized due to possibly sparse data. If multiple records are available, the record closest to the treatment initiation will be utilized.*

Table 1. IMDC risk scores and categories based on two different approaches depending on the data coverage

	IMDC risk category	Total score of IMDC risk factors	Explanations/missing values
Option 1*	Favorable risk	0	no missing values allowed
	Intermediate risk	1-2	1) total score = 1; max 1 risk factor allowed to have missing value 2) total score = 2; no missing values allowed
	Poor risk	3 or more	max 3 risk factors allowed to have missing values
	Unknown risk**	-	when none of the above risk categories can be assigned
Option 2*	Appear favorable	0	all non-missing values for the risk factors indicate favorable risk max 3 risk factors allowed to have missing values
	At least intermediate	≥1	at least one risk factor criterion is met max 3 risk factors allowed to have missing values
	Poor	≥3	at least three risk factor criteria is met max 3 risk factors allowed to have missing values
	Unknown**	-	when none of the above risk categories can be assigned, i.e. more than 3 risk factors have missing value

** If small number of missing values is observed, the option 1 will be selected. If large number of missing values is observed and thus majority of patients were to belong to the “unknown” group of the option 1, the option 2 will be selected. The selection will be done after the data release and monitoring of data coverage.*

*** Patients with unknown risk category, will be analysed as own patient group.*

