7.2. Setting

The target population of this study is adult patients with RCC and medical records available at HDSF data lake. Estimated number of patients in this study is 220-550. The inclusion criteria is a diagnosis of renal cell carcinoma (ICD-10: C64) between January 2010 and December 2021 (Figure 1). Advanced/metastatic disease stage (mRCC) will be assessed based on ICD-10 diagnosis code for metastasis (C77*-C79*), American Joint Committee on Cancer (AJCC) stage 4, visit to oncologist (specialty code 65), or initiation of treatment for mRCC.

[figure not shown]

Figure 1. Graphical illustration of study time windows and corresponding analyses.

The data collected has been generated as part of standard clinical care, treatment, and follow-up of patients with RCC. In accordance with the Finnish Act on Secondary Use of Health and Social Data 552/2019 (in Finnish: Laki sosiaali- ja terveystietojen toissijaisesta käytöstä), health registry data can be processed in scientific studies without patient consent. The purpose of this act is to establish conditions for the effective and secure processing of, and access to, personal health and social data for certain secondary purposes, such as research and statistics, innovation and development, knowledge management, teaching and authority planning. Thus, the Secondary Act creates a clear legal basis for the use of such registered data for research and innovation related to, for example, the health and well-being of citizens, the prevention of

disease and the development of new treatment methods. This relatively new legislation is also a welcome unification of the fragmented Finnish national rules regarding the use of healthcare and social welfare data. In addition, it takes into consideration current data protection requirements.

In the primary objective 1 (characteristics), all RCC patients will be analysed (local and metastatic diseases separately), while in the other objectives only treated mRCC patients will be analysed. Therefore, there are two cohorts to be analysed: 1) characteristics cohort (including all RCC patients), 2) mRCC cohort (including only treated mRCC patients).

Definitions for mRCC cohort

Index: Date of the first mRCC diagnosis; date of the metastatic disease identified as first of the following after the initial RCC diagnosis

- ICD-10 diagnosis code (C77*-C79*) for metastatic disease
- AJCC stage 4
- Visit to oncologist (specialty code 65) with RCC as main diagnosis

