- Treatment initiation for mRCC (sunitinib, pazopanib, cabozantinib, ipilimumab, nivolumab)

When analyzing the treatment outcomes, index is defined as the date of the treatment initiation.

End of follow-up (whichever of the following occurs first):

- Death
- Moving outside of HDSF
 - Approximated using data of healthcare contacts; no contacts to specialty care of HDSF within 2 years (patient censored at the last recorded visit)
- End of study (31.12.2021)

Length of follow-up (in years): ('end of follow-up' – 'index' + 1)/365.25

Definitions for characteristics cohort

Index:

- For mRCC patients, same as for the mRCC cohort (i.e. approximated metastasis date)
- For RCC patients, the date of the first record of RCC diagnosis (ICD-10: C64)

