7.7.5. Healthcare resource utilization

Secondary objective 2:

Healthcare resource utilization (HCRU) will be defined as number of outpatient clinic visits, ER visits, hospitalizations, hospital inpatient days, performed procedures, operations, imaging, and laboratory tests. The price will be evaluated for each entry using publicly available price listings.

The absolute number of each HCRU type and the absolute costs associated will be reported. Additionally, the estimates will be scaled to “per-patient” estimates (by dividing the absolute estimates with the number of contributing patients) and to “per patient year” estimates (by dividing the absolute estimates by the number of contributing patient years).

Additionally, assess the HCRU cumulatively over time, i.e. annual costs per patient during the first 5 years from index, each year separately (i.e., the costs during the first year after the diagnosis of advanced/metastatic RCC, during the second year, etc).

No statistical testing for difference between groups will be performed and estimates will be descriptive in nature. However 95% confidence intervals (CI) for the estimates will be derived using bootstrapping over patients.

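### IMDC strata fixed at first treatment are applied to resource use and morbidity counted from mRCC diagnosis, so year-1 contrasts between strata are partly created by the definition

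*Combined protocol and SAP*

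**What the plan says.** - **Index of the mRCC cohort** (7.2 Setting): "Date of the first mRCC diagnosis; date of the metastatic disease identified as first of the following after the initial RCC diagnosis". The triggers are a metastasis code, AJCC stage 4, an oncologist visit with RCC as main diagnosis, and "Treatment initiation for mRCC (sunitinib, pazopanib, cabozantinib, ipilimumab, nivolumab"). Three of the four can precede treatment. The same section moves the index to treatment start for treatment outcomes only.
- **Cohort** (7.2.2): patients never treated for mRCC are excluded.
- **Stratum** (7.2.3): IMDC category is "defined at the initiation of the first treatment for the metastatic RCC" and is "Applied to all primary and secondary objectives". Factor 1 of the score is "Less than a year from time of initial RCC diagnosis to initiation of treatment for the metastatic RCC". For laboratory values and performance status, "data of ± 3 months around the treatment initiation will be utilized due to possibly sparse data".
- **Time axis of the secondary objectives**: 6.2 asks for resource use accumulated from diagnosis (2a) and by treatment line (2b). Section 7.7.5 costs each of the first five years from index, that is "the costs during the first year after the diagnosis of advanced/metastatic RCC, during the second year, etc". Section 7.7.4 counts patients with each morbidity before and after the mRCC diagnosis, as number and percentage.

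Section 7.7 repeats that all analyses are stratified by IMDC. No landmark or time-varying stratum is planned for the secondary objectives, and the limitations in 7.9 do not mention the issue.

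**The concern.** A stratum should be known when the clock starts. Here the clock starts at mRCC diagnosis and the stratum is known only at first treatment. Selection guarantees survival over the time between, and the length of that time is itself an ingredient of the stratum through factor 1. Favourable patients can therefore spend more of year 1 before treatment than poor-risk patients, for a reason that is purely definitional.

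IMDC category is the plan's main stratification (7.1), so readers will take stratified annual costs, use per patient-year and post-diagnosis infection or antihypertensive percentages as describing prognosis. Part of any difference may instead come from how the strata were formed.

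**Working it through.** **Plan's own figure.** Section 7.5 gives 1,100 RCC patients, of whom 20–50% develop mRCC: 1,100 × 0.20 = 220 and 1,100 × 0.50 = 550, as stated. The point does not depend on this figure.

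**Step 1: date logic.** Let R be RCC diagnosis, X the index and T first mRCC treatment. By 7.2, X is not before R.

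- Factor 1 is scored when T − R < 1 year. Since T − X ≤ T − R, everyone who scores it has T − X < 1 year.
- If the disease is metastatic at RCC diagnosis, X = R. Not scoring factor 1 then means T − X ≥ 1 year: at least a year from index alive and untreated.
- If X − R ≥ 1 year, factor 1 is zero whatever the wait, and this link vanishes.
- If treatment start is itself the first trigger, T − X = 0 and only the post-treatment part of the ±3-month window looks ahead.

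A favourable category needs a score of 0, hence no factor 1, under both options in Table 1. Factor 1 needs only two dates, which every treated patient should have, so the missing-data option chosen does not alter this.

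**Step 2: how common is X = R?** Section 5 gives 20–30% metastatic at diagnosis and another 20% relapsing later. Depending on the base of the second figure, the synchronous share of mRCC runs from 0.20/(0.20 + 0.20) = 50% to 0.30/(0.30 + 0.70 × 0.20) = 0.30/0.44 = 68%. This is a share of all mRCC, not of the favourable stratum. The cohort also admits pre-2010 local RCC that metastasises later (7.2.2), which lowers it.

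**Step 3: effect on one patient's year 1 (assumed use of 1 unit per month before treatment and 3 after).** Take two synchronous patients alive throughout year 1. Treated at 2 months: 2 × 1 + 10 × 3 = 32. Treated at 12 months or later: 12 × 1 = 12. If use does not change at treatment, both total 12.

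**Step 4: null simulation** (1,000,000 patients per scenario; risk has no effect on cost or death). None of these inputs is in the documents: 30% have a zero index-to-treatment gap and the rest an exponential gap with the mean shown; median survival is 24 months; the five other IMDC factors are present at 20% each; mean time from RCC diagnosis to index is 36 months if metachronous. The synchronous share is 50% or 68%, from step 2. Patients dying before treatment are dropped, as 7.2.2 requires. Paired entries are for 50% / 68% synchronous.

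| Mean gap (months) | Treated within 12 months of index: favourable | Same: poor | Poor/favourable year-1 cost per patient, use ×3 | Per patient-year, use ×3 | Per patient, use ×1 |
|---|---|---|---|---|---|
| 2 | 100% / 100% | 100% / 100% | 1.01 / 1.01 | 1.01 / 1.01 | 1.00 / 1.00 |
| 4 | 94% / 91% | 99% / 99% | 1.05 / 1.06 | 1.06 / 1.08 | 0.99 / 0.98 |
| 8 | 77% / 68% | 97% / 97% | 1.15 / 1.22 | 1.18 / 1.26 | 0.97 / 0.96 |
| 12 | 66% / 56% | 94% / 95% | 1.22 / 1.31 | 1.27 / 1.38 | 0.96 / 0.95 |

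The true ratio is 1.00 throughout. With use ×1, the per-patient-year ratio was 1.00. Because 30% have no gap, the mean over all simulated patients is 0.7 times the figure shown (for example 0.7 × 12 = 8.4 months) before early deaths are dropped. With the clock moved to treatment start, both ratios were 1.00 in every scenario.

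**The case against.** The strongest reply has five parts.

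1. **Every stratum is death-free until treatment.** This stands. A reader might infer that only favourable patients enjoy a guaranteed death-free period while others can die from the first weeks. The exclusion of untreated patients in 7.2.2 rules that out: strata differ only in the length of the period. Nor is a one-year wait unique to favourable patients. A synchronous patient treated after a year with low haemoglobin is intermediate and has waited just as long.
2. **The direction is not established.** This stands. A reader might infer that the plan understates early use and drug-related morbidity in the favourable group. The resource items listed in 7.7.5 do not include drugs (Table 2 does link medications to this objective), and a pre-drug year can contain nephrectomy and imaging. Morbidity is counted ever/never over follow-up, so longer guaranteed survival could raise the favourable percentage.
3. **The gap may be short.** This is plausible. Section 7.2.1 says metastasis codes are rarely used and relies on the oncologist visit, and treatment start is itself a trigger. AJCC stage 4 could still date the index earlier. The plan gives no gap, and the effect is negligible at about 2 months.
4. **Output is descriptive.** Correct: 7.7.5 plans no tests between groups, so no false-positive test is at stake. The bootstrap intervals measure precision and would not reveal this distortion.
5. **A treatment-anchored view exists.** Use by treatment line (objective 2b) is not affected in this way, but the annual costs in 7.7.5 are explicitly from diagnosis.

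**Conclusion.** The mismatch of time origin and stratum is in the text, and the tie through factor 1 follows from the dates alone. Year-1 contrasts between IMDC strata in resource use from diagnosis are partly produced by the definition, and the unequal guaranteed interval also enters the stratified post-diagnosis morbidity percentages.

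The size is unknown in advance. Under the assumed inputs, the false poor-to-favourable cost ratio per patient lies between 1.01 and 1.31 if use triples at treatment start, and between 0.95 and 1.00 if it does not change. The documents support neither a fixed direction nor a particular share of favourable patients affected. Use by treatment line, morbidity before index and all unstratified results are not affected in this way. The point should be settled before the data are seen; it does not undermine the study as a whole.

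**What to change.** In 7.2.3, 7.7.4 and 7.7.5:

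- For IMDC-stratified results of objective 2a and of post-index morbidity, start the clock at first-line initiation.
- Keep the from-diagnosis results for the whole treated cohort, unstratified.
- Report use between mRCC diagnosis and first treatment as a separate unstratified interval, and tabulate the length of that interval by IMDC stratum.

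The cost is protocol wording and a changed start date in the code; the dates are already among the variables in Table 2. Two drawbacks should be stated. Stratified costs will no longer run from diagnosis. A small look-ahead also remains, because laboratory and performance values up to 3 months after treatment start may still set the category.

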6.1. Primary objectives

1. Characterize patients with RCC and with advanced/metastatic RCC (treated and non-treated separately) including e.g. demographics and IMDC risk score.
2. Define treatment patterns and treatment sequences in mRCC.
3. Assess outcomes by treatment line and from diagnosis
 - a. Progression free survival (via proxies such as time-to-next treatment)
 - b. Overall survival
 - i. time to event analyses
 - ii. Cox models

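### The IMDC category is defined only at first mRCC treatment, so the untreated mRCC patients whom primary objective 1 must describe by IMDC cannot be classified

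*Combined protocol and SAP*

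**What the plan says.** Section references follow the numbering in the body of the protocol.

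- **Objective.** Section 6.1, primary objective 1: "Characterize patients with RCC and with advanced/metastatic RCC (treated and non-treated separately) including e.g. demographics and IMDC risk score". Section 6 adds that every other objective uses treated mRCC patients only.
- **Anchor.** Section 7.2.3 has the IMDC category "defined at the initiation of the first treatment for the metastatic RCC", and its scope is "Applied to all primary and secondary objectives".
- **Factor 1.** "Less than a year from time of initial RCC diagnosis to initiation of treatment for the metastatic RCC".
- **Factors 2-6.** "for performance status and laboratory values data of ± 3 months around the treatment initiation will be utilized due to possibly sparse data".
- **Unclassifiable patients.** Under Option 2 of Table 1, Unknown applies "when none of the above risk categories can be assigned, i.e. more than 3 risk factors have missing value". Option 1 assigns Unknown when no other category fits. A table note adds: "Patients with unknown risk category, will be analysed as own patient group".
- **Choice of option.** Option 2 replaces Option 1 if missing values would put the majority of patients in the Unknown group of Option 1. The patients to be counted are not specified.
- **Characteristics at index.** Section 7.7.1 summarises laboratory values and performance status within 90 days either side of index, extendable to 6 months. For mRCC patients, index is the approximated metastasis date (Section 7.2), which untreated patients also have. This window is not linked to the IMDC category.

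**The concern.** Primary objective 1 is the only objective that includes untreated mRCC patients, and IMDC risk score is one of the two characteristics it names. The only rule for deriving the category needs a date that these patients lack by definition. Followed as written, the rule yields a single uninformative cell for them.

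There are two further risks. An analyst may fill the gap after data release with an undocumented workaround, and some workarounds produce a category distribution that reflects the definition rather than the patients. In addition, the choice between Options 1 and 2 depends on how many patients are Unknown. If untreated patients are counted, a group that can never be classified could decide which score is used for the treated patients in all other objectives.

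**Working it through.** **1. The plan's own figure.** Section 7.5 gives about 1,100 RCC patients, of whom 20-50% develop mRCC. 1,100 × 0.20 = 220 and 1,100 × 0.50 = 550, which reproduces the stated 220-550. The number untreated is not given. Assuming 10-50% untreated, the range is 220 × 0.10 = 22 to 550 × 0.50 = 275 patients.

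**2. Table 1 applied to an untreated patient, as written.** There is no treatment date, so 6 of 6 factors are missing.

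- Option 1: Favorable needs no missing values; Intermediate allows at most one; Poor needs a score of 3 or more with at most three missing. None applies, so the result is Unknown.
- Option 2: 6 missing exceeds the limit of 3, so the result is Unknown.
- Coding factor 1 as met or as not met still leaves 5 missing, which is Unknown under both options.

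Missing data are not imputed (Section 7.7), so nothing later in the plan changes this.

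**3. A likely workaround.** Suppose factors 2-6 are taken from the index window and are all recorded, while factor 1 stays missing.

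| Factors met, of five | Option 1 | Option 2 |
|---|---|---|
| 0 | Unknown | Appear favorable |
| 1 | Intermediate | At least intermediate |
| 2 | Unknown | At least intermediate |
| 3 or more | Poor | Poor |

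(Under Option 2, scores of 3 or more are read as Poor, since the two upper categories overlap.) Under Option 1, Favorable is impossible and scores 0 and 2 become Unknown. Under Option 2 the lowest category remains and nobody is Unknown.

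**4. Size of the Option 1 effect (illustration).** Assume five complete, independent factors, each with the same prevalence p. None of this comes from the documents. The share Unknown is P(0) + P(2) = (1−p)^5 + 10p²(1−p)³.

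- p = 0.2: 0.328 + 0.205 = 0.532
- p = 0.3: 0.168 + 0.309 = 0.477
- p = 0.4: 0.078 + 0.346 = 0.423

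**5. Effect on the choice of option.** Let u be the untreated share, all of them Unknown. If they are counted, the share of treated patients who must be Unknown for the total to reach one half is (0.5 − u)/(1 − u).

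- u = 0.10: 0.40/0.90 = 44%
- u = 0.40: 0.10/0.60 = 17%
- u = 0.50: 0%

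If only treated patients are counted, the threshold is 50%.

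**6. Index-anchored version.** If factor 1 becomes RCC diagnosis to mRCC index under one year, and factors 2-6 come from the index window with all five recorded, all six factors are available and nobody is Unknown under either option.

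**The case against.** The strongest reply is that little is lost. Section 7.7.1 already describes performance status, hemoglobin, calcium, neutrophils and thrombocytes around index, so five of the six components will be shown for untreated patients. All other objectives use treated patients only. Recorded or text-mined IMDC scores might exist for some untreated patients. IMDC was built on treated patients, so a score without a treatment date is not strictly IMDC.

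Much of this stands, and it limits the size of the point. It does not remove the conflict. The index window is not tied to the category, and the interval variable in Section 7.7.1 also ends at treatment. Text-mining is only a possibility, and Section 7.2.3 has no rule for using a score found that way. If IMDC is not meant for untreated patients, primary objective 1 should not request it for them.

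Three stronger readings are tempting, and the documents do not support them.

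- A reader might infer that a planned comparison of risk between treated and untreated patients is lost. The groups are to be described separately; the tests in Section 7.7.1 are between strata, and the strata in Section 7.2.3 are IMDC category and treatment line.
- A reader might infer that index-date values without factor 1 always remove the favourable category. That holds under Option 1 only.
- A reader might take 100% Unknown as something the plan states. It follows from applying the rule literally; calling the category undefined is equally fair.

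**Conclusion.** The conflict is real and no section resolves it. As written, every untreated mRCC patient is Unknown or undefined under both options of Table 1, so the IMDC part of primary objective 1 cannot be answered for them. That conclusion rests on the rules alone. The count of 22 to 275 patients rests on an assumed 10-50% untreated.

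The direct effect is confined to one descriptive analysis. An indirect effect on the treated analyses arises only if untreated patients count towards the majority rule, which the plan leaves open. The figure of 53% down to 42% Unknown illustrates one workaround under Option 1 and depends on the assumed prevalence of 20-40%, independence and complete data; the plan itself expects the data to be sparse. This should be corrected before data release, but it does not threaten the outcome analyses if the option is chosen on treated patients.

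**What to change.** - For primary objective 1, derive a separately labelled modified IMDC score at mRCC index, in the same way for treated and untreated mRCC patients. Factor 1 is RCC diagnosis to mRCC index under one year; factors 2-6 come from the 90-day index window in Section 7.7.1.
- Keep the treatment-anchored IMDC category for all analyses of treated patients under the other objectives.
- Apply the majority rule for choosing between Options 1 and 2 to treated patients only.
- State that IMDC is not applied to local RCC.

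**Cost.** Some protocol wording and one derived variable, from data already to be collected. The real downside is that treated patients carry two labelled scores that may differ. The interval to index is usually shorter than the interval to treatment, and where it is, factor 1 is met at least as often; the windows for factors 2-6 also differ. The modified score should not be reported simply as IMDC.

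**Minimum alternative.** State that IMDC category is not reported for untreated patients, show the index-date components instead, and leave these patients out of the option choice. This costs only wording, but gives up a composite risk description of the untreated group.
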